## 8.1 Primary study parameter(s)

The primary outcome, incidence of recurrence, is analyzed using survival analysis (Cox-regression) on intention to treat basis. The primary outcome is analysis in the total group, and in the subgroups of patients presenting with a first or recurrent episode of aSBO.

In previous studies, (amongst others: v.d. Beukel et al.) no indications have been found for 'violation' of the assumption for proportional hazards. Stratification is applied on the variables *first episode of aSBO vs. recurrent episode of aSBO*, and *hospital*. No other covariates will be taken into account. We will test two-sided.

After a new surgery for another reason, the risk for aSBO will increase as a consequence of new adhesions that can arise due to this surgical procedure. In this trial, we expect this to be a rare event, and the few times that this will happen, this will probably be spread evenly over the two groups. Therefore, there is no reason for censoring nor removal in the intention-to-treat protocol. Only in the secondary perprotocol analysis these patients will be removed.

## 8.2 Secondary study parameter(s)

Recurrence as per protocol analysis, Quality of life, gastro-intestinal complaints, healthcare and societal costs will be analyzed using mixed-effect models.

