#### 4.4 Sample size calculation

Primary outcome is the time to recurrence measured at two years of prospective follow-up. We will perform a superiority trial. Based on previous literature, we expect 20% recurrence in 2-year with wait-and-see policy (based on a mix of patients with a first and recurrent episode of aSBO) and a 10% recurrence rate after intervention, resulting in a hazard ratio (HR) of approximately 0.47.

We estimated that if 378 patients were randomly assigned in a 1:1 ratio (i.e., 189 per group) to the intervention group or the control group, our study would have 80% power to detect an HR for recurrence of adhesive small bowel obstruction of approximately 0.47 at a two-sided  $\alpha$  level of 0.05. After rounding the total number of patients up, we aim to include a total of 380 patients. Analysis will be performed by intention to treat basis, using survival analysis. We will use cox regression to be able to apply multivariable analysis to account for covariates such as previous episodes of ASBO.

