## 6.6 Follow-up of subjects withdrawn from treatment

Patients withdrawing from the study who randomized to the control arm, or prior the intervention, do not require specific follow-up. Patients withdrawing after the intervention will receive appropriate surgical care. This includes a single outpatient clinic to evaluate recovery at 6 weeks post-operative, as well as care for possible complications of surgery. After full recovery from surgery no specific follow-up is required.

Patient who refrain from surgery after randomization or cross-over from wait-and-see to surgery but do not withdraw from the study as a whole, will be followed according to the study procedures as described above and analyzed based on intention-to-treat.

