#### 8. STATISTICAL ANALYSIS

Data will be analyzed according to the intention-to-treat principle. The primary outcome (difference in incidence of recurrence between groups) will be analyzed using multivariate cox-regression to account for the stratification variables, i.e. first episode vs. recurrent cases; and operating center. Results will graphically be presented using Kaplan-Meier curve.

Surgical findings, and complications in the operative group will be assessed descriptively in a quantitative analysis. Quality of life, gastro-intestinal complaints, healthcare and societal costs will be analyzed using mixed-effect models. Differences with a P-value <0.05 are considered statistically significant.

In case of loss to follow-up, cases are included in survival analysis up to the moment of loss to follow-up. The main potential intercurrent event is abdominal surgery for an indication unrelated to ASBO during follow-up. After this new surgery new adhesions might form that could interfere with the risk of developing an ASBO. Within the 2 year time frame, such unrelated reoperations are expected in approximately 5% of patients. Because of the randomization, we expect both groups to be at equally risk for such event. Our main analysis will be on intention to treat basis, and for this analysis, data from patients with this intercurrent event will be further collected and analysis. As a secondary outcome we will also analysis the data per protocol, in which case patients with intercurrent events are censored.

Another potential intercurrent event is cross-over from the control to intervention group of patients after a recurrence. Patients that cross-over have already reached the primary outcome of a recurrence, and thus this event has no impact on the primary outcome. However, it might impact some of the secondary outcomes. This will be recorded, and accounted for in the secondary analyses.

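### Per-protocol recurrence is censored in section 8, removed in 8.1 and sent to mixed-effect models in 8.2; these instructions cannot all be followed

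*Protocol*

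**What the plan says.** Three places in the Protocol describe the per-protocol analysis of recurrence.

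- **Section 8 (Statistical analysis)** names abdominal surgery unrelated to aSBO as the main potential intercurrent event, expected in about 5% of patients within two years. Under intention to treat these patients stay in with all their data. For the other analysis: "As a secondary outcome we will also analysis the data per protocol, in which case patients with intercurrent events are censored".
- **Section 8.1 (Primary study parameter)** discusses the same surgery. It sees no ground for either censoring or removal under intention to treat, and adds: "Only in the secondary perprotocol analysis these patients will be removed".
- **Section 8.2 (Secondary study parameter)** names the model: "Recurrence as per protocol analysis, Quality of life, gastro-intestinal complaints, healthcare and societal costs will be analyzed using mixed-effect models".

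Elsewhere recurrence is handled as a survival outcome. Section 4.4 describes the primary outcome as time to recurrence, and sections 4.4, 8 and 8.1 all specify Cox regression. Section 8 has its own list of outcomes for mixed-effect models (quality of life, gastro-intestinal complaints, costs), and recurrence is not on it.

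**The concern.** There are two separate faults.

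The first is a conflict over how patients are handled. Censoring at the unrelated surgery keeps the patient's time at risk and any recurrence up to that date. Removal discards the patient altogether. Section 8.1 mentions censoring and removal as distinct operations just before choosing removal, so the two words are not loose synonyms. Removal is the weaker rule: it defines the analysis set by something that happens after randomisation, and it throws away valid information from before the surgery.

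The second is a mismatch of model and endpoint. An ordinary mixed-effect model describes repeated measurements, such as EQ-5D at successive visits. Time to first recurrence is a single time, unobserved in patients whose follow-up ends early. Such a model has no means of carrying out the censoring that section 8 asks for.

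At stake is prespecification. The trial is open label, and a secondary analysis with two handling rules and an unsuitable model leaves a choice to be made once results can be seen. A per-protocol result from a different type of model could also not be set beside the primary hazard ratio.

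**Working it through.** **Inputs**

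- Control recurrence (section 4.4): "we expect 20% recurrence in 2-year with wait-and-see policy".
- Intervention recurrence and hazard ratio (section 4.4): "and a 10% recurrence rate after intervention, resulting in a hazard ratio (HR) of approximately 0.47".
- Planned total: 378, rounded up to 380, allocated 1:1 (section 4.4); 190 per arm.
- Unrelated abdominal surgery: about 5% in two years (section 8).
- Assumed here: constant hazards, and surgery timing independent of recurrence risk and of arm.

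**1. The plan's own figures**

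HR = ln(0.90)/ln(0.80) = 0.472, which matches 0.47. Schoenfeld events for 80% power at two-sided 0.05: 4 × (1.960 + 0.842)² / (ln 0.472)² = 55.8, so 56. With a mean two-year risk of (0.20 + 0.10)/2 = 0.15, 56/0.15 = 373.3, so 374 patients, close to the stated 378. At 378 patients, 378 × 0.15 = 56.7 events are expected and power is 0.807. The sample size reproduces and does not depend on the per-protocol rule.

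**2. Patients concerned**

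0.05 × 380 = 19, or 9.5 per arm.

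**3. Recurrences concerned**

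Patients with both unrelated surgery and a recurrence within two years, if surgery does not change the hazard:

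- Control: 190 × 0.05 × 0.20 = 1.90
- Intervention: 190 × 0.05 × 0.10 = 0.95
- Total: 2.85

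The order of the two events follows from yearly hazards of −ln(0.80)/2 = 0.1116 (control recurrence), −ln(0.90)/2 = 0.0527 (intervention recurrence) and −ln(0.95)/2 = 0.0256 (surgery). The chance that recurrence at time t comes first and surgery follows within two years is the integral from 0 to 2 of λ·exp(−λt)·[exp(−0.0256t) − exp(−0.0513)] dt. Multiplied by 190, this gives 0.98 in control and 0.48 in intervention, 1.46 in total.

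Censoring drops the recurrences after surgery, 2.85 − 1.46 = 1.39. Removal of everyone who has the surgery drops all 2.85. The rules therefore differ by the 1.46 recurrences before surgery, out of 380 × 0.15 = 57 expected.

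**4. Effect on the hazard ratio**

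Under independence, patients retained after removal are those without surgery in two years, and their recurrence hazards are unchanged; under censoring, the hazards before surgery are unchanged. Both rules therefore target 0.472.

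Removal could be read more narrowly, as applying only when surgery comes before any recurrence. No earlier recurrence is then lost, but recurrence-free time is. A simulation of this reading, with 1,000,000 patients per scenario and an assumed recurrence hazard after surgery of 1 or 2 times the earlier one, gave:

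| Hazard after surgery | ITT | Censor | Remove |
|---|---|---|---|
| × 1 | 0.468 | 0.468 | 0.469 |
| × 2 | 0.477 | 0.476 | 0.477 |

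The rules differ by at most 0.001. With an unchanged hazard, the crude two-year control risk moves from 20.0% to 20.5%.

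**5. The model**

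No arithmetic applies. Section 8 asks for censoring, which presupposes a survival method; section 8.2 names a class of models that, in its usual form, has none.

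**The case against.** **Size and standing.** The analysis is secondary, the affected patients are few, and no decision rule in the protocol depends on the result. This stands, and it limits the severity.

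**The model wording.** The mention of recurrence in 8.2 may be a drafting slip, since section 8 has nearly the same sentence without it. A mixed-effects (frailty) Cox model would also handle censoring. Both are possible, but nothing in the protocol says a frailty model is meant, and a slip still needs correcting. It would also be wrong to count three incompatible rules of one kind: there are two conflicting handling rules and one unsuitable model.

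**Leaving it to the SAP.** A protocol may leave much of a per-protocol definition to the SAP. That covers gaps, not this: the protocol states both rules and the model, so any SAP would have to contradict at least one of the three sections.

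**A stronger reading.** A reader might infer that intervention patients who are never operated stay in the per-protocol intervention arm, so that the analysis does not estimate a per-protocol effect and is diluted like intention to treat. The documents do not support this. Section 6.6 speaks of "Patient who refrain from surgery after randomization or cross-over from wait-and-see to surgery but do not withdraw from the study as a whole" and gives only their follow-up and intention-to-treat handling. Section 8 introduces its intercurrent events as potential ones and does not close the list. The protocol gives no rate of non-operation, so any dilution figure would rest on an assumed rate. The full per-protocol set may be defined in the SAP, which is not at hand.

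**Conclusion.** The concern holds as an error in a secondary analysis, of moderate severity. Sections 8 and 8.1 give conflicting rules for the same patients in the same analysis, and section 8.2 assigns a time-to-event outcome to a model class that does not suit it. At the protocol's 5% this touches about 19 of 380 patients and 1 to 2 of some 57 recurrences. The expected change in hazard ratio is negligible, on the assumption that unrelated surgery occurs independently of arm and recurrence risk; a differential pattern could make it larger. The case for correction is therefore prespecification and a usable model rather than a demonstrated bias. The primary intention-to-treat Cox analysis and the sample size stand as they are. The per-protocol status of unoperated intervention patients is unstated, and nothing is concluded from that.

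**What to change.** - **Sections 8 and 8.1:** state one rule. In the per-protocol analysis, keep follow-up and recurrences up to the unrelated abdominal surgery and censor at its date. Delete the instruction to remove these patients.
- **Section 8.2:** take recurrence out of the mixed-effect sentence. State that per-protocol recurrence uses the same Cox model as the primary analysis, adjusted for the stratification factors (first or recurrent episode, and centre).
- **SAP:** confirm that it says how intervention patients who are never operated are treated per protocol. Censoring them at a fixed time would be a separate choice of estimand and could be informative, because those who decline surgery are self-selected; it is not part of this correction.

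The cost is about three sentences. Beyond the date of any unrelated abdominal surgery, which censoring requires in any case, no additional data are needed, and the sample size and primary analysis do not change.

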## **Economic evaluation**

Parallel to the clinical trial an economic evaluation will be performed, comparing the costs and effects of elective adhesiolysis and a watch-and-wait policy, in order to determine the most cost-effective approach. The economic evaluation will be performed from a societal and health care payer perspective, adhering to the Dutch and Belgian guidelines respectively.(17,18) The time horizon of the base case analysis of the economic evaluation will be two years. Some of the long-term consequences of aSBO such as chronic pain can continue to cause morbidity and costs beyond the follow-up of the trial. Also new instances of recurrence of aSBO continue to occur at long periods after surgery, beyond clinical trial follow-up. Long-term cost and effects will therefore be evaluated using decision analytical modeling.

Trial-based economic evaluation

The trial-based cost-effectiveness analysis will be conducted with an intention-to-treat

approach and cost-effectiveness is expressed in (incremental) cost per QALY. Costs of the elective surgery will be calculated based on materials needed, operation time and length of hospital stay. Other important health care cost categories are subsequent hospital visits, related adverse events, readmissions, general practitioner, allied health professional visits, and home care services. There may also be patient and family costs, such as out-of-pocket payments, informal care costs and productivity loss. Most health care use is collected as part of the clinical trial. Data on health care use outside of the hospital, informal care and productivity loss are collected the validated iMTA Medical Consumption Questionnaire (iMCQ) and iMTA Productivity Cost Questionnaire (iPCQ), completed by patients at baseline, 6, 12 and 24 months.(19,20) The questionnaires are modified to include those domains that are potentially impacted by ASBO. The Dutch

manual for costing research is used to determine prices for resource use.(21) The EQ-5D-5L survey is used to calculate QALY using area under the curve calculations.(22) The EQ-5D is completed at baseline, 6, 12 and 24 months.

The differences in costs and QALYs between elective adhesiolysis and the wait-and-see-policy are estimated using regression analyses, accounting for baseline imbalances and the correlation between costs and outcomes.(23) If relevant, an incremental cost-effectiveness ratios (ICER) is calculated by dividing the estimated difference in costs by the difference in QALYs, i.e. ICER =  $\Delta$  costs /  $\Delta$  QALY. Uncertainty in the costs and effect differences and the ICER, is addressed using non-parametric bootstrapping techniques (with 5000 replicates). The probability of elective adhesiolysis being cost-effective, for various ceiling ratios for the ICER (i.e. willingness to pay per QALY gained) is presented in a cost-effectiveness acceptability curve (CEAC). Several scenario and one-way sensitivity analyses will be performed to further assess the robustness of results. Recommended statistical methods are followed and performed in R Studio.(24)

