#### 6.3 Study procedures

Patients who recovered from aSBO by conservative treatment who meet the above inclusion and exclusion criteria are eligible for inclusion. Potential candidates are identified by treating surgeons and physicians at participating operative and referral centres. The treating surgeon or physician will discuss the option of participating in the study and give a short introduction on what participation entails at discharge. Furthermore, the physician will verbally ask permission to the patient for the study team to contact the patient and schedule an outpatient visit to an operative centre to provide full information on the trial and discuss participation, non-committal. Patients referred to discuss participation in the trial will receive written information about the trial at a minimum of 5 days prior to the outpatient clinic meeting. The outpatient clinic meeting will be scheduled within two weeks from discharge when the patient has fully recovered. At the outpatient clinic history taking and physical examination will be performed by a qualified surgeon and anaesthesiologist to confirm eligibility of the patient to participate. Further, detailed information about the intervention will be provided.

Patients who agree to participate in the study will provide written informed consent to be randomized.

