#### Control arm

For patients randomizing to the control arm no specific follow-up care is performed as per usual care.

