The Study Data consist of this protocol, including amendments, the electronic forms for data capture, including the annotations and guidance for use, the electronic data-base of the pseudonymized clinical and non-clinical data collected using data capture, including the log of changes from data entry to database lock, study reports based on these pseudonymized data, and any data or reports generated at a later stage, e.g. based on exploratory analyses or stored samples.

"Foreground" means any Study Data, and any tangible biological, chemical and physical material and inventions, that are generated, acquired, discovered, conceived, developed, created, exemplified or derived as a result of carrying out the Clinical Study, whatever its form or nature, whether it can be protected or not, as well as any Foreground IP. Sponsor acknowledges that the main purpose of the research performed under this Agreement is to generate results that will serve the general public interests, and specifically the interests of the patients and public

healthcare decision making bodies, and, therefore, undertakes not to exploit the Foreground in any way that is or could be detrimental to such interests.

The Sponsor owns the Study Data but provides KCE with a copy of the pseudony-mized database after database lock as well as a royalty-free unrestricted license to use the Study Data for non-commercial public health related purposes as detailed in the Agreement between KCE and the sponsor. If judged appropriate, KCE will introduce the request to the competent chamber of the Information Security Committee and arrange for the data linkage. For the sake of clarity, the linked data are not part of the Study Data. However, KCE will discuss with the Sponsor the results of the analyses and the reporting of the linked data.

Table 1 Overview of Study Procedures

	Screening period	Randomisa- tion	Treatment Period 			Midterm follow-up			Long-term follow-up
	Visit 1		Visit 2	Visit 3	Visit 4	Visit 5	Visit 6	Visit 7	
	Max 2 weeks af- ter dis- charge	Max 4 days after visit 1	Day of Surgery (max. 6 weeks after randomisation)	Discharge (~1-7 days after surgery)	Outpatient clinic (2-6 weeks after surgery)	6 months	12 months	24 months	5 years
Informed consent	Х								
Eligibility Assessment	X 	Х							
Randomisation		Х							
Surgical findings			X						
Registration of Physical examination and history taking 	X				X	Х	Х	Х	

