#### 9.2 Recruitment and consent

Patients are identified by their treating physician or surgeon during admission for aSBO. Patients in whom aSBO resolves with conservative treatment are eligible.

The treating surgeon or physician will discuss the option of participating in the study and give a short introduction on what participation entails at discharge.

The treating physician will verbally ask permission to the patient for the study team to contact the patient and inform further about the trial and schedule an outpatient visit at an operative centre to provide full information on the trial and discuss participation, non-committal. Patients referred to discuss participation in the trial will receive written information about the trial at a minimum of 5 days prior to the outpatient clinic meeting. The outpatient clinic meeting will be scheduled within two weeks from discharge when the patient has fully recovered. Patients who agree to participate in the study will provide written informed consent to participate in the study. Patients remain free to withdraw at will at any time from the study without giving a reason.

Eligible patients that agree to receive detailed information to consider participation will receive the Patient Information Form (PIF), the Informed Consent (IC) form and the patient information brochure from the study team online via e-mail prior (at a minimum of 5 days prior to the outpatient clinic meeting) to the visit to the outpatient clinic. The PIF explains the rationale behind the study, as well as what participation entails. An outpatient clinic appointment at an operative centre is scheduled within two weeks from discharge. During the outpatient clinic meeting, eligibility of the patients will be further assessed by a surgeon and anesthesiologist. The surgeon will also discuss in detail the intervention in the study as well as the prognosis of watchful waiting, and provides a possibility for further questions on the intervention. If patients require more time for a decision about participation a digital follow-up visit is scheduled at 4-5 days. If the patient decides to participate informed consent will be signed digitally or on paper at the outpatient visit, or a digital follow-up visit, by the patient and a representative of the study team.

Version number: 2, 25-04-2025 33 of 44

The intervention will be scheduled at the operative center where the patient has visit the outpatient clinic.

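### The pre-operative surgical and anaesthetic work-up is given to both arms before randomisation and drops out of the cost difference, so the incremental cost of surgery is understated by up to about one work-up per patient

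*Protocol*

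**What the plan says.** The trial-based part of the economic evaluation (Protocol, section 8.2) gives a rule for the operation: "Costs of the elective surgery will be calculated based on materials needed, operation time and length of hospital stay". The next sentence lists what else counts: "Other important health care cost categories are subsequent hospital visits, related adverse events, readmissions, general practitioner, allied health professional visits, and home care services". Patient and family costs follow. The difference in costs between arms is then estimated by regression with adjustment for baseline imbalance, and uncertainty is handled by bootstrapping.

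Section 6.3 describes the visit at which candidates are assessed: "At the outpatient clinic history taking and physical examination will be performed by a qualified surgeon and anaesthesiologist to confirm eligibility". Section 9.2 repeats this: "During the outpatient clinic meeting, eligibility of the patients will be further assessed by a surgeon and anesthesiologist". In Table 1 (Overview of Study Procedures) the randomisation column is timed as "Max 4 days after visit 1". A footnote to that table reserves Visits 2 to 4 for the intervention arm. These are the day of surgery, discharge and the post-operative clinic.

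For the comparator, section 6.3 says: "For patients randomizing to the control arm no specific follow-up care is performed as per usual care". Section 5.1 says the same of wait-and-see in general.

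**The concern.** Being fit for an operation is an entry condition, so every randomised patient has already been seen by a surgeon and an anaesthesiologist. Outside the trial, that work-up is part of offering elective adhesiolysis. The protocol describes nothing comparable for a patient who is simply waiting. A cost that belongs to one strategy is thus incurred equally in both arms by design, and the costing rule does not assign it to the surgical side.

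Cost per QALY is a listed secondary outcome, and the evaluation is meant to identify the more cost-effective approach. An omission that always points the same way enters the cost difference, the ICER and the acceptability curve. Regression, baseline adjustment and bootstrapping cannot recover it, because it does not differ between the arms.

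**Working it through.** The protocol states no figure for this item, so there is none to reproduce. The check is cost algebra followed by a scale.

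**Inputs**
- Content of the surgery cost and of the other cost categories: section 8.2.
- Work-up before randomisation in all patients, with no separate pre-operative visit scheduled afterwards: sections 6.3 and 9.2, Table 1.
- Cross-over from control only after a recurrence: sections 3 and 6.3. Expected two-year recurrence under wait-and-see, 20%: section 4.4.
- Unit cost of the work-up, w: not given. Assumed EUR 100 to 500.
- Cost of the elective operation: not given. Assumed EUR 4,000 to 8,000. The only operative figure is EUR 16,305 for an operated aSBO episode (section 1), which is not an elective cost.

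**Step 1: the difference between arms.** Let S be the costed operation and R the later costs avoided.
- Strategies in practice: (S + w − R) − 0 = S + w − R.
- Trial, work-up costed in both arms: (S + w − R) − w = S − R.
- Trial, work-up costed in neither arm: (S − R) − 0 = S − R.

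The shortfall is w per patient in both cases.

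**Step 2: cross-over.** Let a share c of controls later have the operation. In practice the surgical items differ by (S + w) − c(S + w).
- If no work-up is attributed to anyone, the trial gives S − cS, and the shortfall is (1 − c)w.
- If the controls who cross over have a fresh assessment costed as a later visit, the trial gives S − c(S + w), and the shortfall is w.

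With c at most 0.20 on the planning figure, the shortfall lies between 0.80w and w. That is EUR 80 to 100 at w = 100, and EUR 400 to 500 at w = 500.

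**Step 3: effect on the summary measures.** For a positive QALY gain, the ICER is too low by the shortfall divided by the QALY difference. The incremental net benefit is too high by the shortfall at every ceiling ratio, so the acceptability curve moves towards surgery throughout. The protocol gives no expected QALY difference, so the change in the ICER cannot be computed.

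**Step 4: scale against the operation.**
- Lowest share under the assumptions: 100 / 8,000 = 1.25%.
- Highest share: 500 / 4,000 = 12.5%.
- Against EUR 16,305: 100 / 16,305 = 0.6% and 500 / 16,305 = 3.1%.

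**Step 5: what would shrink it.** A usual-care surgical visit after discharge would put part of w into the comparator legitimately. A pre-operative check repeated after randomisation and costed would put part or all of w into the surgical arm.

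**The case against.** The best reply is that the protocol only summarises the costing. It does not call the three surgery items exhaustive, and it describes the further categories as important ones, not as a closed list. It also commits to Dutch and Belgian guidance and a Dutch costing manual. Unit-cost composition and the handling of protocol-driven visits are often settled in an economic analysis plan.

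Part of this stands. A reader might infer that the surgery cost is strictly confined to three items; the wording does not go that far. But a fuller list would not solve the problem. If Visit 1 is costed for everyone, it still cancels. Only explicit attribution to the surgical strategy changes the difference, and no sentence provides it. Whether the cited guidance would require it cannot be judged from the protocol.

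A reader might also infer that the work-up can never enter the difference. That is too strong. Surgery may follow up to six weeks after randomisation, and peri-operative care follows local practice (section 6.3), so a later check in the surgical arm is possible, though none is scheduled. Nor do the descriptions of wait-and-see rule out every surgical consultation. Sections 1 and 5.1 say that elective adhesiolysis is already used selectively, especially after recurrent episodes.

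The planned scenario and one-way sensitivity analyses could include the work-up, but none is said to do so.

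**Conclusion.** The point holds as a one-sided understatement of modest size. Followed as written, the costing leaves the pre-operative assessment out of the between-arm difference. The incremental cost of surgery is then too low by up to about one work-up per patient. At an assumed EUR 100 to 500 for the work-up, that is roughly 1% to 13% of an operation assumed to cost EUR 4,000 to 8,000. The direction rests on wait-and-see involving no such work-up, as the protocol describes it. The amount falls if usual care includes a surgical visit or if a repeat check is costed. The clinical primary outcome is unaffected.

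Two stronger readings are not supported:
- **That the shortfall is large.** It can be made to look so by comparing it with the hospital savings from a 10-point reduction in recurrence. These run from 0.10 × 2,277 = EUR 228 to 0.10 × 16,305 = about EUR 1,630 per patient. The ICER, however, uses the net cost difference, which includes the operation itself.
- **That the 5-year and lifetime results carry the same error.** The model is informed by trial data, but it also allows reviews, expert interviews, hospital records and data linkage where the trial lacks data. Carry-over is possible but not shown.

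**What to change.** In the trial-based economic evaluation (section 8.2):
- Add the pre-operative surgical and anaesthetic assessment to the defined cost of elective adhesiolysis.
- Charge it once for each patient assigned to the operation and for each control who later crosses over to it, without counting a repeat check twice.
- State that Visit 1 in the control arm is protocol-driven and is not charged.
- Use the same definition wherever the decision model takes the surgery cost from the trial.
- Vary the unit cost in the one-way sensitivity analyses already planned.

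A scenario for patients found unfit is optional. If a share f of those assessed is unfit, the work-up per fit patient is w / (1 − f), for example 1.11w at f = 10% and 1.25w at f = 20% (both assumed). It needs screening counts, which the protocol does not say are collected.

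The main change costs some wording and a unit price, with no new patient data and no change in trial conduct. Its downside is that cost-effectiveness becomes slightly less favourable to surgery.
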